## Table\_2. Statements and Recommendations from the 2005 UK guidelines for the management of Acute Pancreatitis.

1. Diagnosis	! The correct diagnosis of acute pancreatitis should be made in all patients within 48 hours of admission (recommendation grade C).
	
 
The etiology of acute pancreatitis should be determined in at least 80% of cases and no more than 20% should be classified as idiopathic (recommendation grade B).
 

	! Although amylase is widely available and provides acceptable accuracy of diagnosis, where lipase estimation is available it is preferred for the diagnosis of acute pancreatitis (recommendation grade A).
	! Where doubt exists, imaging may be used: ultrasonography is often unhelpful and pancreatic imaging by contrast enhanced computed tomography provides good evidence for the presence or absence of pancreatitis (recommendation grade C).
2. Assessment	! The definitions of severity, as proposed in the Atlanta criteria, should be used. However, organ failure present within the first week, which resolves within 48 hours, should not be considered an indicator of a severe attack of acute pancreatitis (recommendation grade B).
	! Available prognostic features which predict complications in acute pancreatitis are clinical impression of severity, obesity, or APACHE II>8 in the first 24 hours of admission, and C reactive protein>150 mg/l, Glasgow score 3 or more, or persisting organ failure after 48 hours in hospital (recommendation grade B).
	
 
Patients with persisting organ failure, signs of sepsis, or deterioration in clinical status 6– 10 days after admission will require computed tomography (recommendation grade B).
 

3. Prevention of complications	! The evidence to enable a recommendation about antibiotic prophylaxis against infection of pancreatic necrosis is conflicting and difficult to interpret. Some trials show benefit, others do not. At present there is no consensus on this issue.
	! If antibiotic prophylaxis is used, it should be given for a maximum of 14 days (recommendation grade B). Further studies are needed (recommendation grade C).
	! The evidence is not conclusive to support the use of enteral nutrition in all patients with severe acute pancreatitis. However, if nutritional support is required, the enteral route should be used if that can be tolerated (recommendation grade A).

	! The nasogastric route for feeding can be used as it appears to be effective in 80% of cases (recommendation grade B).
4. Treatment of gallstones	! Urgent therapeutic endoscopic retrograde cholangiopancreatography (ERCP) should be performed in patients with acute pancreatitis of suspected or proven gallstone etiology who satisfy the criteria for predicted or actual severe pancreatitis, or when there is cholangitis, jaundice, or a dilated common bile duct. The procedure is best carried out within the first 72 hours after the onset of pain. All patients undergoing early ERCP for severe gallstone pancreatitis require endoscopic sphincterotomy whether or not stones are found in the bile duct (recommendation grades B and C).
	Patients with signs of cholangitis require endoscopic sphincterotomy or duct drainage by stenting to ensure relief of biliary obstruction (recommendation grade A).
	! All patients with biliary pancreatitis should undergo definitive management of gallstones during the same hospital admission, unless a clear plan has been made for definitive treatment within the next two weeks (recommendation grade C).
5. Management of necrosis	! All patients with severe acute pancreatitis should be managed in a high dependency unit or intensive therapy unit with full monitoring and systems support (recommendation grade B).
	! All patients with persistent symptoms and greater than 30% pancreatic necrosis, and those with smaller areas of necrosis and clinical suspicion of sepsis, should undergo image guided fine needle aspiration to obtain material for culture 7–14 days after the onset of pancreatitis (recommendation grade B).
	Patients with infected necrosis will require intervention to completely debride all cavities containing necrotic material (recommendation grade B).
	! The choice of surgical technique for necrosectomy, and subsequent postoperative management, depends on individual features and locally available expertise (recommendation grade B).
6. Provision of services	! Every hospital that receives acute admissions should have a single nominated clinical team to manage all patients with acute pancreatitis (recommendation grade C).
	! Management in, or referral to, a specialist unit is necessary for patients with extensive necrotising pancreatitis or with other complications who may require intensive therapy unit care, or interventional radiological,

	endoscopic, or surgical procedures (recommendation grade B).
--	--

## Table\_3. Statements and Recommendations from the 2018 American Gastroenterological

Association Institute Guideline on Initial Management of Acute Pancreatitis.

1.	!	Recommendation 1A. In patients with AP, the AGA suggests using goal-directed therapy for fluid management. Conditional recommendation, very low quality evidence. Comment: The AGA makes no recommendation whether normal saline or Ringer's lactate is used.
	!	Recommendation 1B. In patients with AP, the AGA suggests against the use of hydroxyethyl starch (HES) fluids. Conditional recommendation, very low quality evidence.
2.	!	Recommendation 2. In patients with predicted severe AP and necrotizing pancreatitis, the AGA suggests against the use of prophylactic antibiotics. Conditional recommendation, low quality evidence.
3.	!	Recommendation 3. In patients with acute biliary pancreatitis and no cholangitis, the AGA suggests against the routine use of urgent ERCP. Conditional recommendation, low quality evidence.
4.	!	Recommendation 4. In patients with AP, the AGA recommends early (within 24 hours) oral feeding as tolerated rather than keeping the patient nil per os. Strong recommendation; moderate quality evidence.
5.	!	Recommendation 5. In patients with AP and inability to feed orally, the AGA recommends enteral rather than parenteral nutrition. Strong recommendation, moderate quality evidence.
6.	!	Recommendation 6. In patients with predicted severe or necrotizing pancreatitis requiring enteral tube feeding, the AGA suggests either nasogastric or nasoenteral route. Conditional recommendation, low quality evidence.
7.	!	Recommendation 7. In patients with acute biliary pancreatitis, the AGA recommends cholecystectomy during the initial admission rather than after discharge. Strong recommendation, moderate quality evidence.

From: Crockett SD, Wani S, Gardner TB, Falck-Ytter Y, Barkun AN; American Gastroenterological Association Institute Clinical Guidelines Committee. American Gastroenterological Association Institute Guideline on Initial Management of Acute Pancreatitis. Gastroenterology. 2018 Mar;154(4):1096-1101. doi: 10.1053/j.gastro.2018.01.032. Epub 2018 Feb 3. PMID: 29409760.

## management of acute pancreatitis.

1. Diagnosis	
 
! The measurement of serum lipase is recommended for the diagnosis of acute pancreatitis. However, when the measurement of lipase is difficult, serum amylase (pancreatic amylase) should be measured. (1B)
 
! 2 Urinary trypsinogen-2 dipstick may be useful for minimally invasive method and rapid diagnosis of acute pancreatitis. However, this is not commercially available in Japan and therefore it cannot be recommended at this time. (ungraded B)
 

2. Diagnostic imaging	
 
! When acute pancreatitis is suspected, ultrasonography is recommended. (1C)
 
! CT is recommended for the diagnosis of acute pancreatitis. (1C)
 
! MRI is more useful than CT in diagnosing bile duct stones causing pancreatitis and hemorrhagic necrotizing pancreatitis. (2C)
 
! Contrast-enhanced CT is useful for the diagnosis of active hemorrhage and thrombosis associated with pancreatitis. (1C)
 

3. Etiology	! During etiological diagnosis, the diagnosis of gallstone-induced acute pancreatitis should be determined as the most important and urgent issue, as this greatly affects the treatment, such as whether endoscopic papillary treatment should be performed or not. (1A)
4. Severity assessment	
 
! In principle, it is recommended that a severity assessment be made immediately after diagnosis and repeated over time (especially within 48 h of the diagnosis). (1C)
 
! It is recommended that a scoring system is used for severity assessments. (1B)
 
! Contrast-enhanced CT is recommended for identifying poorly contrasted areas of acute pancreatitis and is also useful in the diagnosis of complications. However, the possibility of exacerbating pancreatitis and renal function and allergic reactions associated with the contrast must be considered. (2B)
 

5. Transfer indication	! Severe cases should be treated immediately at a facility capable of providing treatment for severe acute pancreatitis. Where such treatment is difficult at the facility, it is strongly recommended that the consideration be given to the immediate transfer of the patient. Even where the case is mild in the early stages, severity assessments should be carried out repeatedly over time, and when the criteria are met, transfer should be considered. (1C)
6. Fluid therapy	
 
! An extracellular solution (Ringer's Lactate solution, etc.) is recommended as the initial infusion solution for acute pancreatitis. (1C)
 
! For patients in shock or with dehydration in the early phases of acute pancreatitis, short-time rapid fluid resuscitation (150–600mL/h depending
 

	
 
on the presence of shock and the dehydration level) is recommended. However, this should be carried out with great care in order to avoid excessive fluid infusion. For patients without dehydration, they should be monitored closely with an appropriate amount of fluid infusion (130– 150mL/h). Particularly for patients with comorbidities such as cardiac or renal failure, the circulating blood volume should be careful evaluated to determine the rate of fluid infusion. (1C)
 
If a mean arterial pressure of 65mmHg or more and a urine output of 0.5mL/kg per h or more has been secured in patients with acute pancreatitis, rapid fluid infusion should be discontinued and a reduction of the rate of fluid infusion is suggested. The volume of infusion should be adjusted to maintain these levels. (2C)
 

7. Nasogastric tube	! No remedial effect of nasogastric tube insertion has been observed for mild acute pancreatitis. Therefore, the routine use of nasogastric suction tubes is not required. (1A)
8. Pain control	Pain associated with acute pancreatitis is severe and persistent, raising the need of sufficient pain control. (1A)
9. Antibiotics prophylaxis	
 
! The prophylactic administration of antibiotics is not necessary in mild acute pancreatitis, since the incidence and mortality rates of infectious complications from mild acute pancreatitis are low. (1A)
 
! The prophylactic administration of antibiotics in severe acute pancreatitis and necrotizing pancreatitis may improve the prognosis, if carried out in the early phases of pancreatitis (within 72 h of onset). (2B)
 
! No remedial effect of the prophylactic administration of antifungal agents for acute pancreatitis has been observed. Therefore, routine administration is not recommended. (1C)
 

10. Protease inhibitor	! The effectiveness of intravenous administration of protease inhibitor (gabexate mesilate) for improving the life prognosis and the rate of complications of acute pancreatitis has not been clearly proven. Further consideration of the efficacy of continuous high-dose intravenous administration for severe cases is required. (ungraded B)
11. Nutritional support	
 
! Intravenous hyperalimentation is not recommended for mild cases. (1B)
 
! Total parenteral nutrition (not performed with oral or enteral nutrition) should be avoided if possible. (1B)
 
! In severe cases, it is more significant as a measure to prevent infection rather than as a route of nutrition support. It can be applied and implemented for severe cases which do not have accompanying intestinal complications. (1A)
 
! If initiated in the early phase, enteral nutrition can reduce the incidence of complications and can contribute to an increased rate of survival. Therefore, it is desirable that it be started within at least 48 h of admission. (2A)
 

	
 
! In principle, it is recommended that enteral feeding tubes be inserted into the jejunum through the Treitz ligament. However, if a feeding tube cannot be inserted into the jejunum, nutrients can be infused into the duodenum or stomach instead. (2B)
 
! The initiation of oral administration should be determined using indicators such as the subsidence of abdominal pain and the serum pancreatic enzyme (especially serum lipase) level, etc. (2B)
 

12. Intensive care	
 
No life-saving effect has been observed from peritoneal lavage for acute pancreatitis, and therefore it is not recommended. (2B)
 
For severe cases where circulation dynamics are not stable with anuria even after sufficient initial fluid infusion or cases with abdominal compartment syndrome (ACS), CHF/CHDF should be introduced. (1C)
 
The efficacy of CHF/CHDF in cases of severe acute pancreatitis not mentioned above is uncertain. Therefore, routine use is not recommended. (2C)
 
Continuous Regional Arterial Infusion therapy is reported to be effective in reducing pancreatic infection and mortality rates for severe acute pancreatitis and acute necrotizing pancreatitis, but its efficacy has not been confirmed. (ungraded B)
 

13. Management of biliary pancreatitis	
 
! Early ERCP/ES should be performed in gallstone-induced acute pancreatitis when complications of cholangitis or prolonged passage disorder of the biliary tract are suspected. (1A)
 
! To prevent the recurrence of gallstone-induced acute pancreatitis, cholecystectomy is recommended for cases where such surgery is possible. (1B)
 
! A cholecystectomy should be performed as soon as gallstone-induced acute pancreatitis has been resolved. (1B)
 

14. Management of abdominal compartment syndrome	
 
The sequential measurement of IAP is recommended for cases with excessive fluid infusion, high severity, renal and respiratory complications, and fluid accumulation in multiple areas as observed by CT, since the onset of ACS increases the mortality rate in such cases. (2C)
 
When there is persistent or recurrent IAPЯ12mmHg, conservative treatment (gastrointestinal decompression, intra-abdominal decompression, improvement of abdominal wall compliance, appropriate fluid infusion and circulation management) should be initiated. The goal should be to manage for IAPIO5mmHg. Surgical decompression should be considered only when internal treatment is not effective for patients with IAP>20mmHg and where the additional complication of organ failure is of concern. (2D)
 

15. Interventions for the local complications	! In principle, conservative treatment should first be performed for necrotizing pancreatitis. The best indication for intervention is applied to cases of infected pancreatic necrosis with suspected or confirmed infection

	
 
accompanying an aggravated general condition. (1C)
 
! Infected pancreatic necrosis should be suspected when clinical symptoms and blood test findings deteriorate. Routine use of FNA is not required for diagnosis, and clinical signs and CT should be used for a comprehensive determination. If an aggravated general condition is observed, percutaneous drainage or endoscopic drainage should be given for diagnosis and treatment. (1C)
 
! If possible, therapeutic intervention for infected pancreatic necrosis should be performed after 4 weeks of onset, when the necrosis has been sufficiently walled off, or in other words, during WON period. (2C)
 
! During therapeutic intervention for infected pancreatic necrosis, percutaneous (retroperitoneal) drainage or endoscopic transluminal drainage should be first given, and if no improvement is achieved, necrosectomy should then be performed. Necrosectomy by endoscopic or retroperitoneal approach is recommended. (2B)
 

16. Post-ERCP pancreatitis	
 
Prophylactic temporary pancreatic stent placement is useful as an effective endoscopic procedure for the prevention of post-ERCP pancreatitis. This should only be performed in the high-risk groups for post-ERCP pancreatitis given the risks and cost. (2A)
 
The guidewire method is very likely to reduce the incidence of post-ERCP pancreatitis. (2A)
 
For the prevention of post-ERCP pancreatitis, the intrarectal administration of NSAIDs should be carried out for all cases undergoing ERCP with no contraindications. (2A)
 
(Other drugs should not be used as routine preventive measures, since their efficacy has been refuted or is uncertain.)
 

17. Clinical indicators (pancreatic bundles)	! A high rate of implementation of the pancreatitis bundles may contribute to improving prognosis of patients with severe acute pancreatitis. (1C)

From: Yokoe M, Takada T, Mayumi T, Yoshida M, Isaji S, Wada K, Itoi T, Sata N, Gabata T, Igarashi H, Kataoka K, Hirota M, Kadoya M, Kitamura N, Kimura Y, Kiriyama S, Shirai K, Hattori T, Takeda K, Takeyama Y, Hirota M, Sekimoto M, Shikata S, Arata S, Hirata K. Japanese guidelines for the management of acute pancreatitis: Japanese Guidelines 2015. J Hepatobiliary Pancreat Sci. 2015 Jun;22(6):405-32. doi: 10.1002/jhbp.259. Epub 2015 May 13. PMID: 25973947.

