#### Secondary outcomes

- ! Early definitive treatment rate in 2019 vs. 2020: defined as treatment in accordance with the current guidelines (cholecystectomy or ERCP with endoscopic sphincterotomy during the same hospital admission or within 2 weeks of discharge)
- ! 30-day hospital readmission rate in 2019 vs. 2020: defined as hospital readmission within 30days from discharge for recurrent biliary AP while awaiting interval cholecystectomy, or due to post-cholecystectomy complications
- ! Predictive factors of morbidity and mortality in patients with biliary AP

The compliance of surgeons to the most up-to-date international guidelines on biliary AP will be assessed through the analysis of the following attitudes:

! Use of scoring systems for the diagnosis and severity grading of biliary AP

- ! Use of lipase dosage (for the diagnosis) and CRP (for the severity grading) during the diagnostic workup
- ! Use of Ultrasound scan, CT scan, MRCP, and endoscopic Ultrasound scan (EUS) in the correct way and timing
- ! Use of early ERCP and sphincterotomy in case of cholangitis and/or choledocholithiasis
- ! Use of percutaneous and/or endoscopic drainage in case of infected pseudocyst or necrosis
- ! Timing of surgical necrosectomy
- ! Timing of re-laparotomy in case of open abdomen strategies
- ! Use of prophylactic antibiotics/antifungals
- ! Use of somatostatin analogs
- ! Use of early enteral feeding
- ! Use of early definitive treatment strategies, including cholecystectomy and/or ERCP and sphincterotomy

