## Section 10 – 30-day Morbidity

- ! Gastric outlet obstruction (Yes/No)
- ! Pseudocyst (Yes/No)
- ! Infected necrosis (Yes/No)
- ! Endoscopic drainage of pseudocyst/walled-off necrosis (Yes/No)
- ! CT-guided fine needle aspiration in case of infected pseudocyst/walled-off necrosis (Yes/No)
- ! Surgical necrosectomy (Yes-laparoscopic/Yes-open/No)
- ! Timing of surgical necrosectomy (< 2 weeks from the onset of symptoms/2-4 weeks)>4 weeks)
- ! Setting of surgical necrosectomy (Upfront/After failure of endoscopic necrosectomy/After failure of endoscopic and percutaneous necrosectomy)
- ! Cystogastrostomy (Yes-endoscopic/Yes-surgical/No)
- ! Abdominal compartment syndrome (Yes/No)
- ! Open abdomen (Yes/No)
- ! Timing of re-exploration (24-48 hours/48-72 hours/>72 hours)
- ! Bleeding (Yes/No)
- ! Bowel ischemia (Yes/No)

- ! Bowel fistula (Yes/No)
- ! Necrotizing cholecystitis (Yes/No)

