16. Enteral nutrition	! Enteral nutrition is recommended to prevent gut failure and infectious complications. Total parenteral nutrition (TPN) should be avoided but partial parenteral nutrition integration should be considered to reach caloric and protein requirements if enteral route is not completely tolerated. Both gastric and jejunal feeding can be delivered safely (1A).
17. Indications for emergent ERCP	
 
! Routine ERCP with acute gallstone pancreatitis is not indicated (grade 1A).
 
! ERCP in patients with acute gallstone pancreatitis and cholangitis is indicated (grade 1B).
 
! ERCP in acute gallstone pancreatitis with common bile duct obstruction is indicated (grade 2B).
 
! ERCP in patients with predicted severe acute gallstone pancreatitis without cholangitis or common bile duct obstruction cannot be
 

	recommended at this time (grade 2B).
18. Indications for percutaneous/endoscopi c drainage of pancreatic collections	
 
Clinical deterioration with signs or strong suspicion of infected necrotizing pancreatitis is an indication to perform intervention (percutaneous/endoscopic drainage)
 

	After 4 weeks after the onset of the disease:
	– On-going organ failure without sign of infected necrosis
	– On-going gastric outlet, biliary, or intestinal
	obstruction due to a large walled off necrotic
	collection – Disconnected duct syndrome
	- Symptomatic or growing pseudocyst
	After 8 weeks after the onset of the disease:
	- On-going pain and/or discomfort (grade 1C)
19. Indications for surgical intervention	! As a continuum in a step-up approach after percutaneous/endoscopic procedure with the same indications
	
 
Abdominal compartment syndrome
 
Acute on-going bleeding when endovascular approach is unsuccessful
 
Bowel ischaemia or acute necrotizing cholecystitis during acute pancreatitis
 
Bowel fistula extending into a peripancreatic collection (Grade 1C)
 

20. Timing of surgery	Postponing surgical interventions for more than 4 weeks after the onset of the disease results in less mortality (2B).

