BEST PRACTICE ADVICE 6	Pancreatic debridement should be avoided in the early, acute period (first 2 weeks), as it has been associated with increased morbidity and mortality. Debridement should be optimally delayed for 4 weeks and performed earlier only when there is an organized collection and a strong indication.
BEST PRACTICE ADVICE 7	Percutaneous drainage and transmural endoscopic drainage are both appropriate first-line, nonsurgical approaches in managing patients with walled-off pancreatic necrosis (WON). Endoscopic therapy through transmural drainage of WON may be preferred, as it avoids the risk of forming a pancreatocutaneous fistula.

BEST PRACTICE ADVICE 8	Percutaneous drainage of pancreatic necrosis should be considered in patients with infected or symptomatic necrotic collections in the early, acute period (<2 weeks), and in those with WON who are too ill to undergo endoscopic or surgical intervention. Percutaneous drainage should be strongly considered as an adjunct to endoscopic drainage for WON with deep extension into the paracolic gutters and pelvis or for salvage therapy after endoscopic or surgical debridement with residual necrosis burden.
BEST PRACTICE ADVICE 9	Self-expanding metal stents in the form of lumen-apposing metal stents appear to be superior to plastic stents for endoscopic transmural drainage of necrosis.
BEST PRACTICE ADVICE 10	The use of direct endoscopic necrosectomy should be reserved for those patients with limited necrosis who do not adequately respond to endoscopic transmural drainage using large-bore, self-expanding metal stents/lumen-apposing metal stents alone or plastic stents combined with irrigation. Direct endoscopic necrosectomy is a therapeutic option in patients with large amounts of infected necrosis, but should be per- formed at referral centers with the necessary endoscopic expertise and interventional radiology and surgical backup.
BEST PRACTICE ADVICE 11	Minimally invasive operative approaches to the debridement of acute necrotizing pancreatitis are preferred to open surgical necrosectomy when possible, given lower morbidity.

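### The CRF cannot show when infected collections were drained or whether the percutaneous route was used, and drainage after day 30 can be recorded as no drainage

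*Combined protocol and SAP*

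**What the plan says.** **Compliance list.** The Secondary outcomes section names one attitude as "Use of percutaneous and/or endoscopic drainage in case of infected pseudocyst or necrosis", with no time attached. The next entry is "Timing of surgical necrosectomy", so for necrosectomy the timing is itself the attitude.

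**CRF.** Section 10, headed "30-day Morbidity", has two drainage fields: "Endoscopic drainage of pseudocyst/walled-off necrosis (Yes/No" and "Cystogastrostomy (Yes-endoscopic/Yes-surgical/No". Neither carries a date. The same section gives surgical necrosectomy three timing classes counted from symptom onset: under 2 weeks, 2 to 4 weeks, and over 4 weeks. Percutaneous drainage has no field. The percutaneous route appears only as a failed prior step in the field on the setting of surgical necrosectomy.

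**Timed statements in the guideline tables.**
- Table 4, item 15: "If possible, therapeutic intervention for infected pancreatic necrosis should be performed after 4 weeks of onset, when the necrosis has been sufficiently walled off".
- Table 5, Best Practice Advice 8, gives an early time for one route: "Percutaneous drainage of pancreatic necrosis should be considered in patients with infected or symptomatic necrotic collections in the early, acute period (<2 weeks".
- Table 1, item 18: one list of indications is headed "After 4 weeks after the onset of the disease", and one further indication applies after 8 weeks.

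**Untimed statements in the same tables.** Table 1, item 18, sets no time where a patient deteriorates with suspected infected necrosis. Table 4, item 15, sets none where the general condition worsens. Table 5, Best Practice Advice 5, sets none for infected necrosis.

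**Use of the item.** The primary objective relates disregarded guideline items to negative outcomes. The Statistical analysis section enters clinical attitudes into logistic models of morbidity and mortality. The Primary outcomes section counts 30-day morbidity from hospital admission. No section says how a CRF answer becomes complied or disregarded, or what to do with drainage after day 30.

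**The concern.** The drainage item feeds the primary objective, but the CRF collects less than the item and the cited recommendations need. There are two consequences.

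First, information is lost. A Yes does not say whether drainage came in week 1, week 3 or week 5, and a percutaneous drainage may leave no trace. Neither gap can be filled at the analysis stage.

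Second, the combination of an undated field, a 30-day heading and a 30-day outcome can bias the comparison. A patient first drained after day 30 has, by definition, survived the 30-day mortality window. If that patient is entered as No, the undrained group gains survivors because of the coding alone. An association between drainage and death could then appear where drainage has no effect.

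**Working it through.** The protocol states no figure on this point, so there is none to reproduce. The check sets the fields against the recommendations, then works out the window, the scale and an illustration of the bias.

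**1. What the CRF can answer**

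| Question raised by the protocol's own text | Answerable from Section 10? |
|---|---|
| Was endoscopic drainage used? | Yes, but not limited to infected collections |
| Was percutaneous drainage used? | No field |
| Was drainage before 2 weeks, or after 4 or 8 weeks, from onset? | No |
| Was drainage before or after day 30 from admission? | No |
| When was surgical necrosectomy done? | Yes, in three classes |

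**2. Days left in the window.** The 4 weeks run from onset and the 30 days from admission (stated for morbidity; assumed the same for mortality). Days left = (30 + lag) − 28 = 2 + lag, where lag is the time from onset to admission. The documents give no lag. An assumed lag of 0, 3 or 7 days leaves 2, 5 or 9 days.

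**3. Share of late drainages that fall inside the window.** Call this share c. The distribution of drainage times after 4 weeks is an assumption.

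| Assumed distribution | Lag 0 (2 days) | Lag 7 (9 days) |
|---|---|---|
| Uniform over weeks 4 to 8 (28 days) | 2/28 = 7% | 9/28 = 32% |
| Exponential, mean 14 days | 1 − exp(−2/14) = 13% | 1 − exp(−9/14) = 47% |
| Exponential, mean 7 days | 1 − exp(−2/7) = 25% | 1 − exp(−9/7) = 72% |

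So c could lie anywhere from about 7% to 72%.

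**4. Scale.** The Background section gives necrotizing disease in up to 20% of cases and some surgical or endoscopic intervention in 38% of those. The Sample size section gives at least 200 per year. 400 × 0.20 × 0.38 = 30.4, so about 30 patients, or 15 per year. The rates are for all acute pancreatitis and any intervention, so this is a rough ceiling at the minimum size.

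**5. Illustration of the bias.** Take 100 collections (a round number for percentages, not an expected count): 40 drained before 4 weeks, 40 after, 20 never. Let 30-day mortality be 30% in the early-drained and the never-drained; the section on pancreatic necrosis gives up to 30% with infection. Let it be 0 in the late-drained, which is exact after day 30 and approximate just before. All splits are assumed.

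- Coded Yes: 40 + 40c patients, 0.30 × 40 = 12 deaths.
- Coded No: 20 + 40(1 − c) = 60 − 40c patients, 0.30 × 20 = 6 deaths.
- Ratio of mortality, Yes to No = [12/(40 + 40c)] / [6/(60 − 40c)] = (3 − 2c)/(1 + c).

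| c | Yes | No | Ratio |
|---|---|---|---|
| 7% | 12/42.8 = 28% | 6/57.2 = 10% | 2.7 |
| 32% | 12/52.8 = 23% | 6/47.2 = 13% | 1.8 |
| 47% | 12/58.8 = 20% | 6/41.2 = 15% | 1.4 |
| 72% | 12/68.8 = 17% | 6/31.2 = 19% | 0.9 |
| 100% | 12/80 = 15% | 6/20 = 30% | 0.5 |

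The ratio is 1 at c = 2/3. Below that, drainage looks harmful; above it, protective. The last row is the case in which every late drainage is entered as Yes: the survivors move to the other group and the bias reverses. Recording late drainage does not by itself repair the analysis.

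**The case against.** A reader might infer that early drainage scores as compliance and postponed drainage as disregard, so that the item runs opposite to the guidelines. The documents do not support this, for four reasons.

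- There is no scoring rule, so any statement about what counts as compliance is inferred.
- Early drainage is not necessarily contrary to the cited guidance. The untimed statements in Tables 1, 4 and 5 cover infected or deteriorating patients. The 4-week line in Table 4 is conditional and graded 2C, while the untimed line just before it is graded 1C. The 4-week list in Table 1 opens with organ failure without signs of infected necrosis.
- The advice for the first 2 weeks concerns the percutaneous route, which has no field. Such a drainage is more likely to be missed than entered as Yes.
- The endoscopic field names pseudocyst and walled-off necrosis, and Table 4 places the walled-off period after 4 weeks. Drainage of an immature collection does not clearly belong there.

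The day-30 cut-off is also uncertain. Section 10 offers an over-4-weeks class for necrosectomy and Section 7 a class beyond 30 days for repeat CT, so some sites may enter later procedures. In addition, a low captured share presupposes a very short lag, and the subgroup is small.

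All of this stands and limits the claim. It does not supply the missing date, the missing percutaneous field or a rule for procedures after day 30. Table 1 also lists symptomatic or growing pseudocysts under its 4-week heading, so the timing question does reach the existing endoscopic field.

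**Conclusion.** The concern holds in a limited form. From the CRF as written, neither the timing of drainage nor use of the percutaneous route can be assessed, although the protocol lists drainage by either route as a compliance attitude and cites timed recommendations for it. This follows from the text alone.

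The bias is conditional. If sites apply the 30-day heading, drainage after day 30 is coded No and the undrained group gains patients who could not have died within the window. That can make drainage look harmful. Its size is unknown, because it depends on an onset-to-admission lag, a distribution of drainage times and a reading of the heading that the documents do not give. If enough late drainage is entered as Yes, the direction reverses.

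At the planned minimum size about 30 of 400 patients are concerned, so the year-to-year comparison is little affected. The drainage item in the primary objective is affected directly. The change is worth making because the lost information cannot be recovered by reanalysis.

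**What to change.** 1. **CRF.** Add a percutaneous drainage field. Give it, endoscopic drainage and cystogastrostomy the classes already used for necrosectomy (No, under 2 weeks, 2 to 4 weeks, over 4 weeks from symptom onset), keeping the route for cystogastrostomy. Add a flag for procedures after day 30 from admission and tell sites to record them.
2. **Compliance list.** Report use and timing of drainage as separate items.
3. **Analysis.** For 30-day outcomes, do not count drainage after day 30 as an exposure. Either use a landmark or time-dependent analysis, or describe the late class without modelling it. The first two need the day of the procedure and the day of death. The CRF records 30-day mortality only as Yes/No, so day counts would have to be added for this subgroup. The descriptive option needs no more than the classes and the flag.
4. **Reconciliation.** State which of the recommendations in Table 1 (item 18), Table 4 (item 15) and Table 5 (Best Practice Advice 5 and 8) defines compliance for each type of collection, and how a CRF answer maps to it. This review takes no position on which clinical timing is right.

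**Cost.** One new field, a few answer options, one flag and a short coding rule. Sites must look past day 30 in the notes of a small subgroup. This is feasible: the last eligible admission is 31/12/2020 and data entry opens on 01/03/2021, 60 days later.
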